11.3 Protocol Deviations

Protocol deviations will be listed only. Protocol deviations will be identified through a review of derivations captured by the Syneos Health site monitors and through programmatic checks on the database.

Protocol deviations include:

- Subjects not meeting eligibility criteria.
- Subjects who have been unblinded.
- Subjects taking prohibited concomitant medications during the study.

Further details will be given in the SAP.

12 QUALITY ASSURANCE AND QUALITY CONTROL

12.1 Audit and Inspection

Study centres and study documentation may be subject to Quality Assurance audit during the course of the study by the Sponsor or its nominated representative. In addition, inspections may be conducted by regulatory authorities at their discretion.

12.2 Monitoring

Data for each subject will be recorded on a CRF. Data collection must be completed for each subject who signs an ICF and is administered IMP.

In accordance with current GCP and ICH guidelines, the study monitor will carry out source document verification at regular intervals to ensure that the data collected in the CRF are accurate and reliable. Appropriate modifications to study conduct, including monitoring and source document verification procedures will be observed, consistent with the FDA Guidance on Conduct of Clinical Trials of Medical Products during the COVID-19 Pandemic; March 2020; the EMA Guidance on the Management of Clinical Trials During the COVID-19 (CORONAVIRUS) Pandemic; Version 4 (04/02/2021); and other local guidance in place at the time of study conduct.

The Investigator must permit the monitor, the IEC/IRB, the Sponsor's internal auditors, and representatives from regulatory authorities direct access to all study-related documents and pertinent hospital or medical records for confirmation of data contained within the CRFs.

12.3 Data Management and Coding

Syneos Health will be responsible for activities associated with the data management of this study. This will include setting up a relevant database and data transfer mechanisms, along with appropriate validation of data and resolution of queries. Data generated within this clinical study will be handled according to the relevant standard operating procedures of the data management and biostatistics departments of Syneos Health.

Study centres will enter data directly into an electronic data capture (EDC) system by completing the CRF via a secure internet connection. Data entered into the electronic case report form (eCRF) must be verifiable against source documents at the study centre. Data to be recorded directly on the eCRF will be identified and the eCRF will be considered the source document. Any changes to the data entered into the EDC system will be recorded in the audit trail and will be FDA CFR 21 Part 11 compliant.

Medical coding will use MedDRA for prior and concomitant diseases, and AEs, and WHODrug for medications.

Missing or inconsistent data will be noted within the EDC system and queried with the Investigator for clarification. Subsequent modifications to the database will be documented.

12.4 Quality Management and Risk Evaluation

Details are provided in [Section 8.3.2](#).

13 RECORDS AND SUPPLIES

13.1 Drug Accountability

On receipt of the IMP, the Investigator (or designee) will conduct an inventory and verify that IMP supplies have been received intact and in the correct amounts before completing the supplies receipt. The Investigator will retain a copy of this receipt at the study centre and send the original receipt to the study monitor. The monitor may check the study supplies at each study centre at any time during the study.

It is the responsibility of the study monitor to ensure that the Investigator (or designee) has correctly documented the amount of the IMP received, dispensed, and returned on the dispensing log that will be provided. A full drug accountability log will be maintained at the study centre at all times. The study monitor will arrange collection of unused IMP returned by the subject's parents/legal guardians. The study monitor will also perform an inventory of IMP at the close-out visit to the study centre. All discrepancies must be accounted for and documented.

13.2 Financing and Insurance

Financing and insurance of this study will be outlined in a separate agreement between Syneos Health and the Sponsor.

14 ETHICS

14.1 Independent Ethics Committee or Institutional Review Board

Before initiation of the study at each study centre, the protocol, the ICF, other written material given to the subject's parent (legal guardian), and any other relevant study documentation will be submitted to the appropriate IEC/IRB. Written approval of the study and all relevant study information must be obtained before the study centre can be initiated or the IMP is released to the Investigator. Any necessary extensions or renewals of IEC/IRB approval must be obtained for changes to the study such as amendments to the protocol, the ICF or other study documentation. The written approval of the IEC/IRB together with the approved ICF must be filed in the study files.

The Investigator will report promptly to the IEC/IRB any new information that may adversely affect the safety of the subjects or the conduct of the study. The Investigator will submit written summaries of the study status to the IEC/IRB as required. On completion of the study, the IEC/IRB will be notified that the study has ended.

14.2 Regulatory Authorities

Relevant study documentation will be submitted to the regulatory authorities of the participating countries, according to local/national requirements, for review and approval before the beginning of the study. On completion of the study, the regulatory authorities will be notified that the study has ended.

14.3 Ethical Conduct of the Study

The Investigator(s) and all parties involved in this study should conduct the study in adherence to the ethical principles based on the Declaration of Helsinki, GCP, ICH guidelines, and the applicable national and local laws and regulatory requirements.

14.4 Informed Consent

The process of obtaining informed consent must be in accordance with applicable regulatory requirement(s) and must adhere to GCP.

The Investigator is responsible for ensuring that no subject undergoes any study-related examination or activity before the parent(s)/legal guardian(s) have given written informed consent for their child to participate in the study.

The Investigator or designated personnel will inform the parent(s)/legal guardian(s) of the objectives, methods, anticipated benefits and potential risks and inconveniences of the study. The parent(s)/legal guardian(s) should be given every opportunity to ask for clarification of any points s/he does not understand and, if necessary, ask for more information. At the end of the interview, the parent(s)/legal guardian(s) will be given ample time to consider the study. The parent(s)/legal guardian(s) will be required to sign and date the ICF. After signatures are obtained, the ICF will be kept and archived by the Investigator in the Investigator's study file. A

signed and dated copy of the subject ICF will be provided to the subject's authorised representative.

It should be emphasised that the parent(s)/legal guardian(s) may refuse permission for their child to enter the study or may withdraw their child from the study at any time, without consequences for their further care or penalty or loss of benefits to which the subject is otherwise entitled. Children of parents(s)/legal guardian(s) who refuse to give or who withdraw written informed consent should not be included or continue in the study.

If new information becomes available that may be relevant to the willingness of the subject's parent(s)/legal guardian(s) to allow continuation of their child's participation in the study, a new ICF will be approved by the IEC(s)/IRB(s) (and regulatory authorities, if required). The parent(s)/legal guardian(s) of the study subjects will be informed about this new information and re-consent will be obtained.

14.5 Subject Confidentiality

Monitors, auditors, and other authorised agents of the Sponsor and/or its designee, the IEC(s)/IRB(s) approving this research, as well as that of any other applicable agency, will be granted direct access to the study subjects' original medical records for verification of clinical study procedures and/or data, without violating the confidentiality of the subjects to the extent permitted by the law and regulations. In any presentations of the results of this study or in publications, the subjects' identity will remain confidential.

15 REPORTING AND PUBLICATION, INCLUDING ARCHIVING

Essential documents are those documents that individually and collectively permit evaluation of the study and quality of the data produced. After completion of the study (end of study is defined as the date of the last visit of the last subject), all documents and data relating to the study will be kept in an orderly manner by the Investigator in a secure study file. This file will be available for inspection by the Sponsor or its representatives. Essential documents should be retained for 2 years after the final marketing approval in an ICH region or for at least 2 years since the discontinuation of clinical development of the investigational product. It is the responsibility of the Sponsor or its representatives to inform the study centre when these documents no longer need to be retained. The Investigator must contact the Sponsor before destroying any study-related documentation. In addition, all subject medical records and other source documentation will be kept for the maximum time permitted by the hospital, institution, or medical practice.

The Sponsor must review and approve any results of the study or abstracts for professional meetings prepared by the Investigator(s). Published data must not compromise the objectives of the study. Data from individual study centres in multicentre studies must not be published separately.

17 APPENDICES

17.1 RSV Clinical Scoring System for Infants with RSV Infection ≥ 1 Month of Age (Parts A and B)

Score	Respiratory Rate (breaths/min)	Wheezing	Retraction of Respiratory Muscles	General Condition
0	< 30	None ^a	None	Normal
1	31-45	Terminal expiration or only with stethoscope	Intercostal only	-
2	46-60	Entire expiration or audible on expiration without stethoscope	Tracheosternal	-
3	> 60	Expiration and inspiration audible without stethoscope	Severe with nasal flaring	Irritable, lethargic, poor feeding

^a If no wheezing is audible due to minimal air entry, score 3.

Severity Grading	
≤ 5	Mild
> 5 but < 9	Moderate
≥ 9	Severe

Reference

[Wang EE, 1992](#)

17.2 ReSVinet Scale for Parental Use

	Item	0 points	1 points	2 points	3 points
1	Feeding intolerance	No	Mild Decreased appetite (the child did not eat the same as normally) and/or presented isolated vomits with or without cough.	Partial Frequent vomits with cough, but the child does not vomit with every intake. Feeding exhausts the child.	Total Child is unable to feed him/herself. The use of a nasogastric tube or parenteral nutrition was required.
2	Medical intervention	No	Basic The child's respiratory secretions required removal, he or she was explored by a physician or received sporadically nebulised medication. Antipyretics were administered.	Intermediate The child required oxygen therapy, underwent a chest X-ray exploration, or a blood sample was extracted. Treatment with nebulised drugs was given regularly.	High The child required respiratory support with a machine. Respiratory support was given through a special mask applied on the nose or mouth or resting on the child's face, or through an endotracheal tube.
3	Respiratory difficulty	No	Mild The child was not breathing normally, but he/she does not seem to have any difficulty when drawing air.	Moderate The child made an effort for breathing. Respiratory noises can be heard without the need of a stethoscope (just approaching the ear to his or her chest).	Severe Respiratory effort was obvious. The child made important movement of his/her chest, the chest even collapses with every movement, and muscles of neck and belly were used. A lot of respiratory noise was heard without approaching the ear to the child's chest.
4	Respiratory frequency	Normal	Mild or occasional tachypnoea The child breathed more rapidly, but the situation was well tolerated, or the respiratory frequency was normalised after removing secretions from respiratory airways or administering nebulised medication.	Prolonged or recurrent tachypnoea The child breathed more rapidly in a more persistent manner, even after receiving nebulised medication or removing secretions from respiratory tract.	Severe alteration The child breathed quickly and superficially, or really deeply. The child was agitated or drowsy.
5	Apnoea	No			Yes The child stopped breathing. It may have been necessary to stimulate him/her in order to regain normal breathing rate.
6	General Condition	Normal	Mild Child did not seem the same as always, but there did not seem to be anything to worry about.	Moderate Child looked ill, and medical examination was required, but it did not feel like a life-threatening situation.	Severe Child was agitated, apathetic, and/or lethargic. He/she required urgent medical attention. There was no need to be a doctor to see that the clinical situation of the child is worrying.
7	Fever	No	Yes, mild rectal or tympanic temperature < 38.5°C, or axillar temperature < 38°C	Yes, moderate rectal or tympanic temperature > 38.5°C, or axillar temperature > 38°C	

17.3 List of Drugs Affecting [CCI] and [CCI]

Guidance regarding potential interactions with concomitant medications

E1. Concomitant Medications Relevant to RSV521

A clinical DDI study (REVC004) studied the effect of RV521 on the exposure of an index CYP3A4 substrate, midazolam, and the effects of a CYP3A4 inhibitor, itraconazole, a PGP inhibitor, verapamil and a CYP3A4 inducer, rifampicin on the exposure of RV521. The study has completed. The study suggests that RV521 can [CCI] the exposure (C_{max} and AUC₀₋₁₂) of [CCI] by approximately [CCI] and [CCI] fold, respectively. The study also demonstrated that the [CCI], [CCI] the exposure (C_{max} and AUC₀₋₁₂) of RV521 by approximately [CCI] and [CCI] fold, respectively and the [CCI], similarly [CCI] the exposure (both C_{max} and AUC₀₋₁₂) of RV521 by approximately [CCI]. Additionally, the [CCI] the exposure (C_{max} and AUC₀₋₁₂) of RV521 by approximately [CCI] and [CCI] fold, respectively.

Therefore, it is anticipated that the exposure of RSV521 may be affected by drugs that [CCI] or [CCI]. Table E1 provides a list of [CCI]. Table E2 provides a list of [CCI]. Patients receiving [CCI] or [CCI] within [CCI] days before the first dose are excluded from enrolment in the study. If patients require any of these medications during the dosing period of the study then they should be withdrawn from the study.

It is also anticipated that RV521 will affect the exposure of some [CCI] substrates that have a narrow therapeutic range as RV521 is shown to be a [CCI]. Table E3 provides a list of [CCI] substrates. Patients receiving drugs which are known to be [CCI] substrates within 2 weeks before the first dose of study treatment are excluded from enrolment in the study.

These lists are not intended to be exhaustive, and similar restrictions will apply to other agents that are known to [CCI] activity or may be affected by [CCI]. If required, please refer to full prescribing information for all drugs prior to co-administration with RSV521.

Table E1 [CCI] which may increase exposure to RSV521 and are prohibited in the study

[CCI]	[CCI]	[CCI]
[CCI]	[CCI]	[CCI]
[CCI]	[CCI]	[CCI]
[CCI]	[CCI]	[CCI]
[CCI]	[CCI]	[CCI]
[CCI]	[CCI]	[CCI]
[CCI]	[CCI]	[CCI]
[CCI]	[CCI]	[CCI]
[CCI]	[CCI]	[CCI]

[CCI]
[CCI]
[CCI]
[CCI]

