8.4.4 Removal of Subjects from Therapy or Assessments

Subjects may be withdrawn from the study for any of the following reasons:

- Parent/legal guardian request
- Use of prohibited concomitant medication/therapy

- Non-compliance with the protocol
- Lost to follow-up
- Occurrence of AEs that are not compatible with the continuation of the subject in the study, in the Investigator's opinion, or that make it unacceptable to the subject's parent/legal guardian for them to continue
- Investigator request
- Intercurrent illness
- Sponsor request
- Becoming critically ill with respiratory insufficiency leading to the requirement for mechanical ventilation/positive airway pressure (PAP)/high-flow oxygen
- Randomisation code broken prematurely (Parts B and C)

Parents/legal guardians are free to withdraw their children from the study at any time without providing reason(s) for withdrawal and without prejudice for receiving further treatment. The reason(s) for withdrawal will be documented in the case report form (CRF). Parents/legal guardians who choose to withdraw their child from the study will be encouraged to allow their child to complete the same final evaluations as subjects completing the study according to the protocol, particularly safety evaluations.

All reasonable efforts should be made to contact the parent/legal guardian of a subject who is lost to follow-up. These efforts must be documented in the subject's file.

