8.5.6.2 Prohibited Medication/Therapy

The following medications/therapy will not be permitted during the study:

- Palivizumab or treatment with any antiviral therapy for RSV (eg, ribavirin or IV immunoglobulin)
- Corticosteroids (oral, IV, or inhaled)
- Heliox
- Leukotriene receptor antagonists (eg, montelukast)
- Exogenous surfactant
- Mucolytics
- Any drug, which could impact on the PK of the investigational product including potent inhibitors or moderate or potent inducers of CYP P450s (for details see Appendix 17.3).
- Herbal preparations/medications are not allowed throughout the study. These herbal medications include, but are not limited to CCI, kava, ephedra (ma huang), ginkgo biloba, dehydroepiandrosterone (DHEA), yohimbe, saw palmetto, and ginseng.
- Consumption of CCI-containing products are not allowed throughout the study. CCI.

Subjects who need to start treatment with prohibited medications during the study will be required to discontinue study treatment, but must remain in the study according to the post-study drug treatment period specified in the Schedule of Assessments, and should also attend the follow-up visit. After the end of their participation in the study, each subject will be treated according to standard clinical practice.

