9.4.5 Post Treatment (Part C)

Visit Day 7 (40 – 48 Hours Post-Dose 10) Follow-up:

Note: Visit Day 7 may occur on Study Days 7 or 8 depending on when the subject received his or her first dose of IMP.

- Physical examination
- Evaluation of hydration status
- Body weight/length/head circumference
- Vital signs (body temperature, systolic and diastolic BP, HR, RR)
- 12-Lead ECG
- Record RSV-related signs and symptoms, and severity (if indicated), including: temperature, cough, coryza, grunting with expiration, nasal flaring, retractions, and wheezing
- ReSVinet scale for clinicians ([Appendix 17.6](#))
- Adapted ReSVinet Scale for Parental use ([Appendix 17.2](#))
- Safety laboratory tests (clinical chemistry and haematology)
- Urinalysis
- PK blood sample according to sampling schedule in [Table 5](#)
- Nasopharyngeal swab
- Concomitant medication review
- Adverse event review

Visit Day 14 Follow-up:

- Vital signs
- Body weight/length/head circumference
- Record RSV-related signs and symptoms, and severity (if indicated), including: temperature, cough, coryza, grunting with expiration, nasal flaring, retractions, and wheezing
- ReSVinet scale for clinicians ([Appendix 17.6](#))
- Adapted ReSVinet scale for parental use ([Appendix 17.2](#))
- Nasopharyngeal swab
- Concomitant medication review
- Adverse event review

Visit Day 34 Follow-up:

- Vital signs
- Body weight/length/head circumference
- Record RSV-related signs and symptoms, and severity (if indicated), including: temperature, cough, coryza, grunting with expiration, nasal flaring, retractions, and wheezing

- ReSVinet scale for clinicians ([Appendix 17.6](#))
- Adapted ReSVinet scale for parental use ([Appendix 17.2](#))
- Nasopharyngeal swab
- Concomitant medication review
- Adverse event review

Early Withdrawal (or Discontinuation) Visit

Parents/legal guardians who withdraw their child from the study will be encouraged to allow their child to complete the same final evaluations as subjects completing the study according to this protocol (ie, at the relevant post-treatment visit), particularly safety evaluations.

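### For drugs that alter RV521 exposure, Protocol 8.5.6.2 keeps the child in the study while Appendix 17.3 withdraws the same child, and 8.4.4 does not settle which rule applies

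*Protocol*

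**What the plan says.** Protocol 8.5.6.2 (Prohibited Medication/Therapy) includes in its list "Any drug, which could impact on the PK of the investigational product including potent inhibitors or moderate or potent inducers of CYP P450s" and refers to Appendix 17.3 for the details. For a child who has to start any prohibited drug, it requires study treatment to stop and the child to stay: "but must remain in the study according to the post-study drug treatment period specified in the Schedule of Assessments". It also asks for attendance at follow-up.

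Appendix 17.3 covers the same class of drugs. The title of its Table E1 describes them as ones "which may increase exposure to RSV521 and are prohibited in the study". The drug names are redacted, but the rule is legible: "If patients require any of these medications during the dosing period of the study then they should be withdrawn from the study".

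Protocol 8.4.4 lists "Use of prohibited concomitant medication/therapy" among the reasons for which a subject may be withdrawn. The section is permissive. It does not separate stopping study drug from leaving the study, and it gives neither of the other two sections precedence.

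**The concern.** A child who needs a Table E1 or E2 drug during dosing falls under both rules at once, and they point in opposite directions. The synopsis plans about 75 centres in about 15 countries, so two sites that each follow the protocol can handle identical children differently.

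At stake are the assessments after the child leaves. In Part C the post-treatment visits are Day 7, Day 14 and Day 34. Day 7 matters most, for two reasons:

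- Its swab is the closing point of the time-weighted average change in viral load (DAVG), the primary endpoint (Protocol 11.1.3).
- Tables 3a and 3b schedule safety bloods and urinalysis only at Screening and Day 7. Clinically significant laboratory change is part of a Part C secondary endpoint (Protocol 7.2). Table E1 concerns drugs that can raise RV521 exposure, so a missing laboratory result is unwelcome in just these children.

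**Working it through.** **1. The rules side by side**

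| Source | Trigger | Study drug | Study participation |
|---|---|---|---|
| 8.5.6.2 | needs a prohibited drug, including the Appendix 17.3 class | stop (mandatory) | remain (mandatory) |
| Appendix 17.3 | needs a Table E1/E2 drug in the dosing period | ends with withdrawal | withdraw (directive) |
| 8.4.4 | use of a prohibited drug | not addressed | withdrawal allowed |

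The first two rows cannot both be obeyed. The third is compatible with either, so it does not decide between them. The overlap is limited to need arising in the dosing period, because the appendix rule is limited to that period.

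**2. What the appendix route can lose in Part C (Table 3a, optional swabs excluded)**

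- Required swabs for a child in hospital throughout: before Doses 1, 3, 5, 6, 7 and 9, then Days 7, 14 and 34, which is 9. Three are post-treatment. The swabs before Doses 7 and 9 are required only in hospital, so for a child discharged after Dosing Visit 3 it is 3 of 7.
- Only one of those three, Day 7, lies in the DAVG window.
- Safety bloods and urinalysis: 1 scheduled post-baseline occasion, and that one is at risk.

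What is kept: adverse-event follow-up to Day 34 (Protocol 10.1.3.1) and all data before withdrawal (SAP 6.3).

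**3. Size for the primary endpoint (illustration only)**

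Inputs: planned DAVG of -1.5 on placebo and -2.5 on active, SD 1.25 and 34 evaluable per arm (Protocol 11.2). SAP 10.2.1 computes DAVG on the swabs available and divides by the period they cover. On the 12-hourly schedule Dose 10 falls at 9 × 12 = 108 h, so Visit Day 7 falls at 148 to 156 h. I use 156 h.

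Assume a linear decline, so that DAVG up to time T is proportional to T. Take a child with six doses whose last swab is at 72 h:

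- Ratio 72/156 = 0.46. A planned -1.5 is scored -0.69, and -2.5 is scored -1.15.
- Shift in the arm mean per child: (1.50 - 0.69)/34 = 0.024, or (2.50 - 1.15)/34 = 0.040 log10.
- Standard error of a difference between two arms: 1.25 × √(2/34) = 0.303.

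A decline that flattens with an assumed half-time of 36 h gives a ratio of 0.67 and shifts of 0.015 and 0.024. An earlier exit shifts more, but with steady decline not beyond 1.5/34 = 0.044 or 2.5/34 = 0.074.

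**4. Why no recovery figure follows from staying in the study**

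Visit Day 7 is defined as 40 to 48 h after Dose 10 (Table 3a and Protocol 9.4.5). A child who stops early has no Dose 10. Under linear decline, the share of the planned DAVG that is scored depends on when the swab is taken and what happens off drug:

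- Swab at 156 h, decline continues: 1.00.
- Swab at 104 h (44 h after Dose 6, which is at 60 h), decline continues: 104/156 = 0.67.
- Swab at 156 h, decline stops at 72 h: with slope s, area 0.5 × 72 × 72s + 72s × 84 = 8,640s. Divided by 156 this is 55.4s, against 78s for the full decline, so 0.71.

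The documents fix neither the timing nor the off-drug course.

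**The case against.** The strongest reply is that the body of the protocol already gives a workable default. Section 8.5.6.2 is mandatory and treats the appendix as detail. The appendix calls itself guidance and uses weaker language, and it may simply have meant withdrawal from treatment. That is a fair guess at intent. But the appendix refers to the study, 8.5.6.2 shows that the protocol does distinguish the two, and no order of precedence is stated.

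Four stronger readings are tempting, and the documents do not support them.

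- *All three visits are certainly lost.* This is the worst case. Protocol 8.4.4 says that parents "who choose to withdraw their child from the study will be encouraged to allow their child to complete the same final evaluations", and the matching block in 9.4.5 has a heading that also covers discontinuation. The text of both addresses parents who withdraw their child, so it does not secure these visits after a withdrawal under the appendix. Nothing forbids the assessments either.
- *The child goes unmonitored while taking both drugs.* RV521 stops under either rule, so only residual exposure is at issue. Protocol 10.1.3.4 requires follow-up of significant abnormalities and a repeat of invalid post-treatment tests, but neither replaces a test that was never taken.
- *The primary result is biased by a known amount, and 8.5.6.2 would repair it.* Step 4 shows why not. Also, SAP 10.2.1 belongs to a SAP that still describes a two-arm Part C of about 120 subjects, and Protocol 11.1 provides for amending it.
- *The same defect forces out children who deteriorate.* The 8.4.4 item "Becoming critically ill with respiratory insufficiency leading to the requirement for mechanical ventilation/positive airway pressure (PAP)/high-flow oxygen" is permissive, and 8.5.6.1 contemplates ventilated children on study. Whether that wording should be clearer is a separate question. The substrates that 8.5.6.1 permits, such as fentanyl, are also outside this conflict.

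**Conclusion.** Wrong as written: two contradictory instructions for the same child, with nothing to rank them. That conclusion rests on the text alone and needs no assumption.

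The severity is minor to moderate. A site that follows the appendix may lose the Day 7 swab and the only scheduled post-baseline laboratory and urine tests for that child. How many children this concerns is unknown, because the drug lists are redacted and no rate of use is given. Per child, the illustrated shift in an arm mean is 0.015 to 0.040 log10 against a standard error of 0.303, so the effect on the primary comparison is probably small. Those shifts assume the planned DAVG values, the stated curve shapes, a last swab at 72 h and the current SAP rule for missing swabs.

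**What to change.** Three changes of wording:

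1. In Appendix 17.3, replace the instruction to withdraw the child with: *discontinue study treatment but remain in the study (see Section 8.5.6.2)*.
2. Make the prohibited-medication item in 8.4.4 say the same, so that it is a reason to stop study drug and not by itself a reason to leave the study.
3. State that for a child who stops dosing early, the Day 7 swab and safety laboratory tests are taken on Study Day 7 to 8, unless consent is withdrawn. Say that the days are counted from the first dose, because SAP 6.2 counts study days in Parts B and C from randomisation.

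The cost is amendment text with ethics approval, which can travel with the next amendment. It adds no visit or procedure, since the assessments kept are already in the Schedule.
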